6.4.1 Analyses of Primary Efficacy Endpoint

For the primary efficacy parameter (ACR20 response rate at EOT), the Fisher's exact test will be used to compare each JTE-051 dose group with placebo. Furthermore, the exact Cochran-Armitage trend test will also be performed, using the ordinal score for treatment, e.g., score 1 for placebo, score 2, 3, 4 and 5 will be used to represent JTE-051 50 mg, 100 mg, 150 mg and 200 mg, respectively.

Model (Fisher's exact test, will be performed by k=2, 3, 4, 5 separately)

```
proc freq data=xxx;
  table ARC20*trtn/chisq exact; ***trtn is the ordinal score for treatment***;
  where trtn in (1, k);
run;
```

Model (exact Cochran-Armitage trend test)

```
proc freq data=xxx;
  table ARC20*trtn/trend measures ci
    plots=freqplot(twoway=stacked);
  test smdr;
  exact trend;
run;
```

In addition, logistic regression model-based analyses will be performed for the pairwise comparisons between JTE-051 and placebo groups (Model 1) and for the evaluation of dose response relationship (Model 2). The logistic regression models will include the baseline PGA score, hs-CRP and region as a covariate.

Model 1 (pairwise treatment vs placebo comparison)

```
proc logistic data=xxx descending;
  class regionn hscrpn;
  model ACR20 = PGA Dose_50 Dose_100 Dose_150 Dose_200 regionn hscrpn;
run;
```

Model 2 (dose-response analysis)

```
proc logistic data=xxx descending;
  class regionn hscrpn;
  model ACR20 = PGA Dose regionn hscrpn;
  oddsratio Dose;
run;
```

Note:

- In Model 1, Dose_x = 1 if dose=x; otherwise. Dose_x=0; i.e., Dose_x is a dummy variable.
- In Model 2, Dose = 0, 50, 100, 150, 200 for placebo and each JTE-051 dose level, respectively.
- ACR20 is a 0, 1 variable; i.e., ACR20=1 represents a responder; ACR20=0 represents a non-responder.
- Regionn=0 represents 'EMEA'; Regionn=1 represents 'Latin America' or 'North America'.
- Hscrpn=0 represents screening hs-CRP<=2 x upper limit of normal (ULN); Hscrpn=1 represents screening hs-CRP>2 x ULN.
- From the model fitting, one obtains adjusted odds ratios and corresponding p-values for the respective pairwise treatment comparison versus placebo.

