3.7.7. Randomization

Approximately 250 eligible subjects with active RA will be randomized into this study. Subjects will be randomized in a 1:1:1:1:1 ratio (50 subjects per treatment group) to receive JTE-051 50 mg, JTE-051 100 mg, JTE-051 150 mg, JTE-051 200 mg or placebo once daily. Randomization will be stratified by region and by the screening hs-CRP level (the qualifying hs-CRP value must be utilized).

An IWRS will be employed for the randomization activities. It will use a stratified randomization algorithm that takes into account the strata specified above.

The randomization code will be controlled by an unblinded member of the Sponsor or designee who will provide the randomization code to select laboratories, see Section [3.7.8](#).

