6.1 Sample Size

Approximately 250 eligible subjects (50 in each treatment group) are randomized into the DB treatment period of this study.

The primary efficacy evaluation will be to compare the ACR20 response rate between JTE-051 with placebo at EOT. From one study comparing mavrilimumab with placebo in combination with stable MTX, the ACR20 of mavrilimumab and placebo at Week 12 were 0.69 and 0.40, respectively. Assuming the ACR20 of at least one of the JTE-051 doses to be at least 0.30 above placebo, the following sample size per group will be needed to detect a statistical significant difference at the 5% level with about 80% power (using 2-sided Fisher's exact test):

Placebo ACR20	0.25	0.35	0.45
Sample size per group	47	48	47

About 50 randomized subjects per group would therefore give at least an 80% power for a range of placebo responses. The sample size calculation was carried out using the software SiZ 6.2 (Cytel Inc., 2013).

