6.4.2 Analyses of Secondary Efficacy Endpoints

For dichotomous secondary efficacy parameters, similar analyses as the primary efficacy parameter will be used by time point, i.e., the Fisher's exact test for pairwise comparisons with placebo and the Cochran-Armitage test for trend.

For continuous efficacy parameters, the mixed model with fixed effects for treatment, time, treatment by time interaction, the stratification factors and the baseline, and measurements within each subject as repeated measures will be used.

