6.4.3 Supportive Analyses of Efficacy Parameters

For dichotomous efficacy parameter analysis with multiple time points, a supportive analysis will be performed using a generalized estimating equation (GEE) method on the logit scale. The model includes effects for treatment, time, treatment by time interaction, stratification factors and subject as the repeated factor. The odds ratio (OR) of each JTE-051 dose group relative to placebo at the same time point will be estimated.

Model: (generalized estimating equation (GEE) method on the logit scale)

```
proc genmod data=xxxx;
  class usubjid trtn(ref=1) region(ref=0) hscrpn(ref=0);
  model SAEP=trtn time trtn*time regionn hscrpn;
  repeated subject=usubjid/type=un corrw;
run;
```

[figure not shown]
Note: SAPE denotes any dichotomous efficacy parameter, regionn and hscrpn are stratification factors, we can add other stratification when needed.

The supportive efficacy parameters utilizing the non-hs-CRP will be analyzed in a similar manner as their secondary efficacy counterparts using hs-CRP.

All analyses will be performed two-sided at the 5% significance level. No formal multiple comparison adjustment will be made; therefore, results should be interpreted with the multiplicity in mind. The estimated treatment effect (relative to placebo), e.g., odds ratio, from the model, along with a two-sided 95% confidence interval (CI) and p-value, will be tabulated where appropriate. The Newcombe's CI of the rate difference between JTE-051 dose and placebo will be computed when performing the Fisher's exact test. Graphical presentations of the treatment profile will be depicted for the primary and key secondary analyses. Sensitivity analysis and model fit assessment may be conducted, and data transformation may be employed if appropriate.

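### The primary ACR20 tests and the rate-difference interval leave out the randomisation strata: a modest loss of efficiency that is cheap to recover, not an error of validity

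*SAP*

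**What the plan says.** **Randomisation.** Protocol 3.7.7: "Randomization will be stratified by region and by the screening hs-CRP level". SAP 3 gives the levels: EMEA, Latin America and US for region; up to 2 x ULN or above it for hs-CRP. That makes six strata.

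**Primary tests.** SAP 6.4.1: "the Fisher's exact test will be used to compare each JTE-051 dose group with placebo". It adds a trend test: "Furthermore, the exact Cochran-Armitage trend test will also be performed, using the ordinal score for treatment". The printed PROC FREQ code crosses response with treatment only. Protocol 3.8.3.2 names the same tests.

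**Interval and level.** SAP 6.4.3: "The Newcombe's CI of the rate difference between JTE-051 dose and placebo will be computed when performing the Fisher's exact test". No stratified form is named. Also there: "All analyses will be performed two-sided at the 5% significance level".

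**By-visit responder endpoints.** SAP 6.4.2 uses "the Fisher's exact test for pairwise comparisons with placebo and the Cochran-Armitage test for trend", again without strata.

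**Where the strata do enter.** SAP 6.4.1: "In addition, logistic regression model-based analyses will be performed for the pairwise comparisons", followed by a dose-response model. Both models contain baseline PGA, hs-CRP stratum and region, but region is coded in two levels (EMEA against the Americas). The mixed models (SAP 6.4.2) and the GEE (SAP 6.4.3) also include the stratification factors.

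**The concern.** Balanced allocation within strata makes the difference between arms less variable than a crude test assumes, if the strata predict response. The crude test then rejects too rarely, and the crude interval is wider than its label. With about 50 subjects against 50 per comparison, some of the precision bought by stratifying goes unused.

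The plan adjusts for the strata in its other efficacy models. The exceptions are the tests named first for the primary endpoint and the by-visit responder tests. The additional logistic models do not fill the gap for the effect measure: they yield odds ratios, while the reported rate difference and its interval stay crude.

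**Working it through.** **1. Reproduce the plan's figures.** Inputs from SAP 6.1: two-sided 5% Fisher test, +0.30 over placebo ACR20 of 0.25, 0.35 or 0.45, and 47, 48 or 47 per group. Exact power = sum over x, y of Bin(x; n, p0) x Bin(y; n, p1) x 1[Fisher p <= 0.05].

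- At 47/48/47: 79.9% in all three cases, so about 80% is confirmed.
- At 50 per group: 83.5%, 82.8% and 83.5%.
- At the cited 0.40 v 0.69 with 50 per group: 80.0%.
- True size at 50 per group, same placebo rates: 3.0% to 3.4%.

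**2. Why the crude test is conservative.** Let stratum k have share w_k and response rate p_k, with overall rate p. With balance within strata, the null variance of the difference is (2/n) Σ w_k p_k(1-p_k). The crude test uses (2/n) p(1-p). Their ratio is 1-ρ², where ρ² = Σ w_k(p_k-p)² / [p(1-p)].

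Example (assumed): stratum sizes per arm 12, 13, 6, 7, 6, 6; p = 0.35; stratum rates 0.12, 0.30, 0.26, 0.51, 0.46, 0.72.

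- Numerator: 0.24(0.0529) + 0.26(0.0025) + 0.12(0.0081) + 0.14(0.0256) + 0.12(0.0121) + 0.12(0.1369) = 0.0358.
- ρ² = 0.0358/0.2275 = 0.157, so ρ is about 0.40.
- The crude score test then has an effective critical value of 1.96/√0.843 = 2.13, a true size of about 3.3%. Simulation gives 3.2%.

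**3. Simulated size and power, pairwise.** Set-up: 50 v 50, the six strata above balanced across arms, overall rates at the plan's values. Stratum effects are assumptions, given as odds ratios across the extreme regions / across hs-CRP. Ranges are over placebo 0.25 to 0.45. With m_k responders among 2n_k subjects in stratum k, and Y_k of them on active drug, CMH uses Z = Σ(Y_k - m_k/2) / √Σ m_k(2n_k-m_k)/[4(2n_k-1)].

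| Odds ratios (ρ) | Fisher size | Crude score size | Fisher power | CMH power | Stratifying alone (crude score to CMH) | Fisher to CMH |
|---|---|---|---|---|---|---|
| 1/1 (0) | 3.0-3.5% | 4.9-5.6% | 83-84% | 87-88% | -0.5 to 0 | 4.3 to 4.6 |
| 3/2 (about 0.25) | 2.5-2.8% | 4.2-4.8% | 84% | 89-90% | 0.3 to 0.7 | 4.9 to 5.3 |
| 6/3 (about 0.39) | 1.8-2.2% | 3.2-3.7% | 85% | 91-92% | 1.5 to 2.3 | 6.3 to 6.8 |

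Gains are in percentage points. CMH size is 4.9% to 5.5% throughout. Replacing Fisher by an exact conditional stratified test, which stays exact, gains 0, 0.6 to 1.4 and 2.6 to 3.5 points in the three rows (4,000 runs each).

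**4. Trend test and interval.** Five arms of 50, linear rise of 0.20 to the top dose, continuity-corrected as an approximation to the exact test.

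| Odds ratios | Crude trend size | Power gained by stratifying |
|---|---|---|
| 1/1 | 4.3-4.4% | about 0 |
| 2/1.5 | 4.0-4.2% | 0.9 to 1.5 |
| 3/2 | 3.6-3.8% | 2.5 to 3.4 |
| 6/3 | 2.8-3.0% | 6.0 to 7.2 |

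Without the continuity correction, stratifying costs up to about half a point when the strata do not matter. If only the top dose works (+0.30), the gain at 6/3 is 3.4 to 4.9 points (for example 78.8% to 83.4% at placebo 0.35). Coverage of the crude Newcombe interval is 94.4% to 95.2% at 1/1 and 96.3% to 96.8% at 6/3.

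**The case against.** The case for leaving the plan alone has real force. The sample size was calculated for the two-sided Fisher test, so design and analysis match, and Fisher power was at least 82.6% in every stratified scenario. Type I error is protected. Adjusted pairwise and dose-response p-values for the same endpoint are already specified, and collapsing region there costs under 1 point of power in simulation. Stratifying alone adds under 1 point to a pairwise comparison at moderate stratum effects. CMH is asymptotic, and six strata leave roughly 6 to 13 subjects per arm in each. For a rare response (5% v 20%), a check found no gain: 66-67% for the crude score test, 65-67% for CMH. Balance within strata is also assumed, since Protocol 3.7.7 gives no block size.

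All of this stands, and it limits the size of the point. It does not remove it: the first-named tests and the only rate difference still omit factors used in the randomisation, and the trend test loses more than the pairwise tests.

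Three stronger readings are tempting, and the documents do not support them.

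- A reader might infer that the primary analysis is invalid or the trial underpowered. The error is conservative and planned power is met.
- A reader might blame the strata for the whole shortfall below 5%. Fisher's size is already 3.0% to 3.5% with no stratum effect.
- A reader might assume a correlation of 0.5 and infer that 80% power becomes 90%. No correlation is given anywhere. A value near 0.4 already needs stratum rates from 0.12 to 0.72, and the starting power at 50 per arm is about 83%. Protocol 1.3 gives comparable hs-CRP distribution across arms as the reason for stratifying; it does not say that hs-CRP or region predicts ACR20.

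**Conclusion.** The point holds as an efficiency improvement. The Fisher test, the exact trend test and the Newcombe interval omit the randomisation strata, and no stratified rate difference is planned.

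For an assumed stratum-response correlation of 0 to 0.4, stratifying alone is worth about -0.5 to +2.5 points of pairwise power and about -0.5 to +7 points for trend. Changing from Fisher to CMH is worth about 4 to 7 points in total, most of it from leaving the exact test. Fisher's true size is 3.0% to 3.5% with no stratum effect and about 2% with strong strata.

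These sizes rest on assumed stratum sizes and odds ratios, near-balanced allocation within strata and 50 evaluable subjects per arm.

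**What to change.** In SAP 6.4.1:

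- Make the CMH test, stratified by region in the three levels used for randomisation and by screening hs-CRP stratum, the primary comparison of each dose with placebo.
- Report the Mantel-Haenszel rate difference with a stratified Newcombe interval, and amend the interval sentence in SAP 6.4.3 to match.
- Use the stratified CMH correlation statistic with scores 1 to 5 for trend.
- Keep Fisher and the exact Cochran-Armitage test as sensitivity analyses.

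In SAP 6.4.2, carry the stratified tests to the by-visit ACR responses, with an exact stratified version where ACR50 or ACR70 tables are sparse.

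Cost: SAP wording and minor code, with no new data or subjects. Protocol 3.8 lets the SAP modify the plan and says that a major change to the primary analysis may also go into a protocol amendment. The change should be fixed before unblinding. Two downsides: the primary test becomes asymptotic (simulated size about 4.9% to 5.5%), and up to about 1 point of power is lost against an unstratified score test if the strata do not predict response. Against Fisher there was no loss in any scenario in the table.

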3. STUDY DESIGN

This is a multicenter, randomized, double-blind, placebo-controlled, parallel-group, 12-week study in biologic and kinase inhibitor treatment-naïve RA subjects on stable background non-biologic DMARD therapy, including MTX.

Eligible subjects are randomized at Visit 2 to receive JTE-051 50 mg, 100 mg, 150 mg, 200 mg or placebo once daily for 12 weeks. Subjects continue to receive up to two non-biologic DMARDs, including MTX throughout the study (at a stable background dose and route of administration for at least 12 weeks prior to Visit 2 and throughout the study) and return for a Follow-up Visit approximately four weeks after the last dose of study drug is administered. Subject randomization are stratified by geographical region (Europe, the Middle East and Africa [EMEA], Latin America, [LA] and the United States [US]) and by the screening high-sensitivity C-reactive protein (hs-CRP) ($\leq 2 \times \text{ULN}$, $> 2 \times \text{ULN}$).

The study duration will be of approximately 20 weeks per subject:

- Up to a 28-day Screening Period
Note: Certain pre-defined exceptions that would allow for a longer duration of the screening period to ensure a 28-day pre-randomization stabilization of concomitant medications are permitted, as described in Section 3.5.4.1 of the protocol.
- A 12-week double-blind Treatment Period
- Approximately a 4-week Follow-up Period

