6.4.7 Treatment by Center Effect

The randomization in this study is stratified by region (US, LA and EMEA) and by the screening hs-CRP level. Center effect is not considered due to the expectation that many centers will be used and only a small number of subjects will be enrolled in most centers. The region effect will be assessed with respect to the primary efficacy parameter and may be included in the analysis model where appropriate.

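### Region is randomised at three levels but coded at two in the adjusted ACR20 models and the GEE; using the three randomised levels is a free improvement

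*SAP*

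**What the plan says.** SAP section 3 describes randomisation as "stratified by geographical region (Europe, the Middle East and Africa [EMEA], Latin America, [LA] and the United States [US" and by screening hs-CRP, cut at 2 x ULN. SAP 6.4.7 repeats the three regions: "The randomization in this study is stratified by region (US, LA and EMEA) and by the screening hs-CRP level".

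For ACR20 at end of treatment, SAP 6.4.1 gives two sets of analyses.

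- **Unstratified tests.** "the Fisher's exact test will be used to compare each JTE-051 dose group with placebo", followed by an exact Cochran-Armitage trend test. Neither uses strata, in text or in code.
- **Additional logistic models.** Model 1 is pairwise and Model 2 is dose-response. "The logistic regression models will include the baseline PGA score, hs-CRP and region as a covariate". The Note to these models defines the region variable: "Regionn=0 represents 'EMEA'; Regionn=1 represents 'Latin America' or 'North America". It codes hs-CRP at the randomised cut.

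Elsewhere:

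- SAP 6.4.3 (GEE for dichotomous endpoints over several time points) states that "regionn and hscrpn are stratification factors". It gives no other definition of `regionn`, so the one in 6.4.1 applies. Its CLASS statement lists `region`, while its MODEL statement uses `regionn`.
- SAP 6.4.2 (mixed model for continuous endpoints) says only "the stratification factors and the baseline", without a coding.
- SAP 6.4.7 adds: "The region effect will be assessed with respect to the primary efficacy parameter and may be included in the analysis model where appropriate". It names no method or coding.

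**The concern.** The usual principle is to analyse by the factors used to randomise. Here one factor (hs-CRP) follows it and the other (region) does not. Latin America and the US were separate strata at randomisation but share one level in the models, and North America is not a randomised level. A variable labelled a stratification factor in 6.4.3 is therefore not the one used to randomise. Because 6.4.2 leaves the coding open, the continuous endpoints could be adjusted for three regions and the dichotomous ones for two.

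What is at stake is the precision and meaning of the adjusted odds ratios. If Latin America and the US have different ACR20 rates, a model that merges them leaves part of a known prognostic difference unexplained. In logistic regression this pulls the treatment odds ratio toward 1 and makes the test slightly conservative. If the two regions respond alike, nothing is lost.

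**Working it through.** **1. The plan's own figure.** Inputs from SAP 6.1: two-sided Fisher test at 5%, +0.30 over placebo rates of 0.25, 0.35 and 0.45. Exact power is the sum over all (x, y) of Bin(x; n, p0) × Bin(y; n, p0 + 0.30), counting tables with Fisher p ≤ 0.05.

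| Placebo rate | Stated n per group | Power at stated n | Power at n = 50 |
|---|---|---|---|
| 0.25 | 47 | 0.799 | 0.835 |
| 0.35 | 48 | 0.799 | 0.828 |
| 0.45 | 47 | 0.799 | 0.835 |

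The sample size reproduces. It rests on the unstratified test, so region coding does not touch it.

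**2. Region coding, place by place.**

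| Place | Region levels |
|---|---|
| Randomisation (SAP 3, 6.4.7) | 3: EMEA, LA, US |
| Fisher, Cochran-Armitage (6.4.1) | none |
| Logistic Models 1 and 2 (6.4.1) | 2: EMEA v the rest |
| GEE (6.4.3) | 2, through the same variable |
| Mixed model (6.4.2) | not stated |

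Model 1 has an intercept, PGA, four dose terms, one region term and one hs-CRP term: 1 + 1 + 4 + 1 + 1 = 8 parameters. Three-level region makes 9.

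**3. Size of the effect in Model 1.** The documents give no region shares or regional response rates, so all of these are assumed: 250 subjects, blocks of 5 within six strata, hs-CRP split 50/50, every dose at +0.30, baseline PGA left out, 20,000 simulated trials per scenario. The hs-CRP odds ratio (OR) was 1.5, 2 and 3 in the rows with a LA v US OR of 2.2, 4 and 8. Power for one dose v placebo at a placebo rate of 0.35, merged v three-level:

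| LA v US | Shares 55/30/15 | Equal shares | Shares 75/20/5 |
|---|---|---|---|
| Alike (both OR 2 v EMEA) | 0.883 v 0.884 | 0.881 v 0.882 | 0.873 v 0.874 |
| OR 2.2 | 0.868 v 0.871 | 0.869 v 0.874 | 0.864 v 0.866 |
| OR 4 | 0.876 v 0.886 | 0.882 v 0.896 | 0.875 v 0.880 |
| OR 8 | 0.891 v 0.908 | 0.896 v 0.924 | 0.890 v 0.897 |

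Over placebo rates of 0.25 to 0.45 (0.25 and 0.45 run for the first two sets of shares only):

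| LA v US | Power gain from three levels (points) | Merged OR below three-level OR | Trials where significance differs | Type I error, merged |
|---|---|---|---|---|
| Alike | 0.0 to 0.1 | – | – | – |
| OR 2.2 | 0.2 to 0.6 | 1–4% | 0.4–0.7% | 4.4–5.0% |
| OR 4 | 0.5 to 1.4 | 3–10% | 0.8–1.5% | 4.0–4.8% |
| OR 8 | 0.7 to 2.8 | 6–21% | 1.2–2.8% | 3.5–4.7% |

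Three-level type I error was 4.6–5.3% throughout. The two models are fitted to the same trials, so the standard error of a power difference is at most √(d/20,000), where d is the share of trials in which significance differs. For d = 0.007 that is 0.06 point; for d = 0.028 it is 0.12 point.

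**4. A smaller check under different assumptions.** Shares of EMEA/LA/US 60/20/20 or 40/30/30, EMEA placebo rate 0.35, one active dose with log OR 1.24, neither hs-CRP nor PGA, 2,000 trials each. The implied LA v US OR is the ratio of the placebo odds, for example (0.45/0.55)/(0.25/0.75) = 2.45.

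| LA, US placebo rates | LA v US OR | Power, merged v three-level, 60/20/20 | Same, 40/30/30 |
|---|---|---|---|
| 0.35, 0.35 | 1 | 0.880 v 0.880 | 0.882 v 0.882 |
| 0.45, 0.25 | 2.45 | 0.851 v 0.851 | 0.862 v 0.862 |
| 0.55, 0.20 | 4.89 | 0.852 v 0.853 | 0.831 v 0.831 |
| 0.65, 0.15 | 10.5 | 0.795 v 0.801 | 0.750 v 0.792 |

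Type I error was 0.035–0.051 merged and 0.042–0.059 three-level. The pattern is the same: next to nothing at modest differences, up to 4.2 points at a more extreme one.

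**The case against.** The strongest reply is that nothing decision-bearing changes. The logistic models are introduced as additions to the Fisher and trend tests, the merged model holds its size, and a model with fewer terms is defensible if one region is small. All of this stands, and it is why the point is an improvement and not an error.

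The attenuation argument also needs care. A comparison of merged with three-level estimates is not a comparison with the truth. At a LA v US OR of 2.2 (placebo 0.35, shares in the order of the first table in step 3), the true conditional ORs were 3.56, 3.60 and 3.53. The merged medians were 3.56, 3.61 and 3.57, and the three-level medians 3.63, 3.79 and 3.62. At OR 4 with shares 55/30/15 the truth was 3.79, merged 3.70, three-level 3.94. So at modest differences the merged estimate is at least as close. Part of the gap is non-collapsibility: leaving out a covariate changes which conditional OR is being estimated. A clear disadvantage appears at OR 4 with equal regions and at OR 8 in two of the three sets of shares.

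A reader might infer more than the documents support:

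- **That the primary analysis is compromised.** It is not: the Fisher and trend tests never use region.
- **That the pooling was chosen after seeing data.** The SAP states it openly and is written prospectively; section 4.4 refers to steps before the randomisation code is released. Nothing readable suggests otherwise.
- **That the plan has no reason for pooling.** Some subsections (5.2.3–5.2.4, 6.4.5–6.4.6) are not visible in the public SAP, so the statement holds for the readable text only.
- **That 6.4.1 and 6.4.7 conflict on including region.** 6.4.7 gives a general permission; 6.4.1 is a specific case that requires it.
- **That North America misplaces subjects.** US and Latin American subjects both fall in level 1 under either label; only the naming is inconsistent.

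**Conclusion.** The mismatch is real and confined to the region factor: three levels at randomisation, two in logistic Models 1 and 2 and in the GEE, and an unstated coding in the mixed model. The consequence is a small loss of power in additional and supportive analyses. It is about 0 to 0.6 point if the LA v US OR is at most 2.2, and up to about 3 points at 8, with clear attenuation of the adjusted OR only when the two regions differ strongly. No document suggests that they do.

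The sizes rest on assumed region shares, regional effects and hs-CRP effects, and are for Model 1 without its PGA term; the GEE and mixed model were not simulated. In none of the power comparisons above did three-level coding do worse than merging. This is a free improvement: it follows the groups already randomised and leaves the primary test, its stated power and the sample size as they are.

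**What to change.** Before unblinding, amend the SAP as follows.

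1. In 6.4.1, code `regionn` at the three randomised levels (EMEA, LA, US) for Models 1 and 2, keeping it in the CLASS statement. Replace North America with the randomised label.
2. In 6.4.3, use the same coding and list `regionn`, not `region`, in the CLASS statement. With a 0/1 variable the slip is harmless; with three numeric levels outside CLASS, region would enter as a linear score.
3. In 6.4.2, state that the stratification factors in the mixed model take the same coding.
4. If a region may prove very small, add a pooling rule now, to be applied to blinded overall counts: a minimum count and which regions would merge. For scale, a region with 5% of 250 subjects has 0.05 × 250 = 12.5 subjects, or 2.5 per arm.

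The cost is a few lines of text and code and one more parameter per model (9 instead of 8 in Model 1, with about 250 subjects). No new data are needed.
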